7.2. Adverse Events and Deaths

7.2.1. Adverse Event Dictionary

Clinical and laboratory AEs will be coded using the current version of MedDRA. System organ class (SOC), high-level group term (HLGT), high-level term (HLT), preferred term (PT), and lowest-level term (LLT) will be provided in the AE dataset.

7.2.2. Adverse Event Severity

Adverse events are graded by the investigator as Grade 1 (mild), Grade 2 (moderate), Grade 3 (severe) or Grade 4 (life threatening) according to toxicity criteria specified in the protocol. The severity grade of events for which the investigator did not record severity will be categorized as "missing" for tabular summaries and data listings. The missing category will be listed last in summary presentation.

7.2.3. Relationship of Adverse Events to Study Drugs

Related AEs are those for which the investigator answers "Related" to the question "Related to Study Treatment?" in the CRF. Events for which the investigator did not record relationship to study drug will be considered related to study drug for summary purposes. However, by-subject data listings will show the relationship as missing.

7.2.4. Serious Adverse Events

Serious adverse events (SAEs) will be identified and captured as SAEs if AEs met the definitions of SAE specified in the study protocol. Serious adverse events captured and stored in the clinical database will be reconciled with the SAE database from the Gilead Drug Safety and Public Health (DSPH) Department before data finalization.

7.2.5. Treatment-Emergent Adverse Events

In this study, Treatment-emergent adverse events (TEAEs) are defined for the study treatment subject received during Part 1, Co-Administration, and Whole Study periods separately.

7.2.5.1. Definition of Treatment-Emergent Adverse Events

TEAEs for a given administration period are defined as 1 or both of the following:

- Any AEs with an onset date on or after the start date and no later than the data cutoff date of the administration period as defined in Table 7-1.
- Any AEs leading to study drug premature discontinuation during that administration period (ie, the study drug premature discontinuation date is on or after the start date of the period and no later than the period end date as defined in Table 7-1).

7.2.5.2. Incomplete Dates

If the onset date of the AE is incomplete and the AE stop date is not prior to the start date of an administration period, then the month and year (or year alone if month is not recorded) of onset determine whether an AE is treatment emergent during that period. The event is considered treatment emergent during an administration period if both of the following 2 criteria are met:

- The month and year (or year) of the AE onset is the same as or after the month and year (or year) of the start date of the period, and
- The month and year (or year) of the AE onset is the same as or before the month and year (or year) of the data cutoff date of the period

An AE with completely missing onset and stop dates, or with the onset date missing and a stop date on or after the start date of an administration period, will be considered to be treatment emergent of the period. In addition, an AE with the onset date missing and incomplete stop date with the same or later month and year (or year alone if month is not recorded) as the start date of an administration period will be considered treatment emergent of the period.

7.2.6. Summaries of Adverse Events and Deaths

The number and percentage of subjects who experienced at least 1 TEAE will be provided and summarized, using Safety Analysis Sets, by PT and treatment group and overall for each of Part 1, Co-administration, and Whole Study periods respectively. For other AEs described below, summaries will be provided the same as TEAE:

- Any Grade 3 or 4 treatment-emergent AEs
- Any Grade 2, 3, or 4 treatment-emergent AEs
- All treatment-emergent study drug-related AEs
- All treatment-emergent SAEs
- All treatment-emergent study drug-related SAEs
- All treatment-emergent AEs that caused premature discontinuation from HIV study drug
- All treatment-emergent AEs that caused premature discontinuation from LDV/SOF (for co-administration and whole study periods only)

A brief, high-level summary of AEs described above will be provided for Safety Analysis Sets, by treatment group and overall, and by the number and percentage of subjects who experienced the above AEs during each of Part 1, Co-administration, and Whole Study periods respectively. Treatment-emergent deaths observed in the study will be also included in this summary.

Treatment-emergent death at an administration period refers to deaths that occurred between the start date of the period and the data cutoff date of the period.

Multiple events will be counted only once per subject in each summary. Adverse events will be summarized and listed by PT in descending order of total frequency during Co-administration period. For summaries by severity grade, the most severe grade will be used for those AEs that occurred more than once in an individual subject during each analysis period.

In addition, data listings will be provided for the following:

- All AEs
- Grade 3 and 4 AEs
- SAEs
- Deaths report
- AEs leading to premature discontinuation of study drug

7.2.7. Additional Analysis of Adverse Events

7.2.7.1. AIDS-Indicator Conditions

On an ongoing basis, AEs will be reviewed for events that might meet the definition of AIDS-indication conditions that are indicative of an AIDS-Defining Diagnoses (see Protocol Appendix 6). The Gilead medical monitor will review the possible AIDS-indication conditions and approve the events that meet the definition. Events that meet the definition of an AIDS-indication condition will be listed.

7.3. Laboratory Evaluations

Summaries of laboratory data will be provided by-visit for both Whole Study and Part 2 periods using Safety Analysis Sets, unless specified otherwise. Laboratory data collected during the study will be analyzed and summarized using both quantitative and qualitative methods. The analysis will be based on values reported in conventional units. When values are below the LOQ, they will be listed as such, and the imputed value will be used for the purpose of calculating summary statistics as specified in Section 3.7.

A by-subject listing for laboratory test results will be provided by subject ID number and visit in chronological order for hematology, serum chemistry, urinalysis, and urine chemistry separately. Values falling outside of the reference range and/or having a severity grade of 1 or higher on the Gilead Grading Scale for Severity of Adverse Events and Laboratory Abnormalities will be flagged in the data listings, as appropriate.

No inferential statistics will be generated.

7.3.1. Summaries of Numeric Laboratory Results

In summary of numeric laboratory results for Whole Study and Part 2 periods, descriptive statistics (n, mean, standard deviation, median, Q1, Q3, minimum, and maximum) will be provided for each laboratory test specified in the study protocol by treatment group and overall as follows:

- Baseline values
- Values at each postbaseline analysis window
- Change from baseline to each postbaseline analysis window
- Percentage change from baseline to each postbaseline analysis window (if specified)

For Whole Study period, the baseline refers to Study Baseline. The postbaseline visits are counted from Study Day 1. For the Part 2 period, the baseline refers to Part 2 Baseline as defined in Section 3.8.1. And the postbaseline visits in Part 2 of the study (Weeks 12, 16, 20) are re-counted from Week 8 visit and presented as Weeks 4, 8, 12 in by-visit summaries of laboratory data.

The mean, median, Q1, Q3, minimum, and maximum values will be displayed to the reported number of digits; SD values will be displayed to the reported number of digits plus 1.

Median (Q1, Q3) of the observed values for estimated GFR, ALT, and AST will be plotted using a line plot by treatment group and visit.

In the case of multiple values in an analysis window, data will be selected for analysis as described in Section 3.8.3.

Metabolic Assessments

For metabolite assessments, including fasting glucose and the lipid panel (ie, total cholesterol, triglycerides, LDL, HDL, total cholesterol to HDL ratio), only those measurements under fasting status will be summarized by treatment group and overall.

Calcium Corrected for Albumin

Calcium corrected for albumin will be calculated and summarized. The following formula will be used when both serum calcium and albumin results for a given blood draw are available and serum albumin value is < 4.0 g/dL.

• Calcium corrected for albumin (mg/dL) = serum calcium (mg/dL) + $0.8 \times (4.0 - \text{albumin (g/dL)})$

Toxicity grading for calcium will be applied based on the corrected values.

7.3.2. Graded Laboratory Values

The Gilead Grading Scale for Severity of Adverse Events and Laboratory Abnormalities will be used for assigning toxicity grades (0 to 4) to laboratory results for analysis. Grade 0 includes all values that do not meet the criteria for an abnormality of at least Grade 1. For laboratory tests with criteria for both increased and decreased levels, analyses for each direction (ie, increased, decreased) will be presented separately.

If there is any laboratory toxicity grading scale overlapping with the normal reference ranges (eg, grade 1 scale overlaps with normal reference ranges), laboratory values that are within the normal range will be grade 0, except for lipid tests.

For triglycerides, LDL, and cholesterol, the protocol-specified toxicity grading scale is for fasting test values, so nonfasting lipid results (or lipid results without a known fasting status) will not be graded or summarized by toxicity grades.

7.3.2.1. Treatment-Emergent Laboratory Abnormalities

Treatment-emergent laboratory abnormalities will be presented for each of Part 1, Co-administration, and Whole Study periods respectively. Treatment-emergent laboratory abnormalities within each administration period will be summarized by treatment group and overall using Safety Analysis Set.

Treatment-emergent laboratory abnormalities in an administration period are defined as values that increase at least one toxicity grade from baseline (Study Baseline for Part 1 and Whole Study periods, Part 2 Baseline for Co-administration period) at any time postbaseline, up to and including the safety cutoff date of the administration period. If the relevant baseline laboratory data are missing, then any abnormality of at least Grade 1 up to the safety cutoff date will be considered treatment emergent in the administration period.

For serum glucose, fasting glucose and nonfasting glucose are graded based on different grading criteria as specified in the protocol. Treatment-emergent laboratory abnormalities will be summarized for fasting glucose. Since nonfasting glucose was not assessed at Study Baseline, the maximum postbaseline grade instead of treatment-emergent laboratory abnormalities will be summarized for Part 1 and Whole Study period. For consistency, the maximum post Part 2 baseline grade instead of treatment-emergent laboratory abnormalities will be summarized for Co-administration period.

7.3.2.2. Summaries of Laboratory Abnormalities

The following summaries (number and percentage of subjects) for treatment-emergent laboratory abnormalities during Part 1, Co-administration, and Whole Study periods will be provided by treatment group and overall for each lab test; subjects will be categorized according to the most severe postbaseline abnormality grade within the administration period for a given lab test:

- Treatment-emergent laboratory abnormalities
- Treatment-emergent Grade 3 and 4 laboratory abnormalities

For all summaries of laboratory abnormalities in an administration period, the denominator is the number of subjects with nonmissing postbaseline values up to safety cutoff date of the period.

A by-subject listing of treatment-emergent Grade 3 or above laboratory abnormalities will be provided by subject ID number and visit in chronological order.

7.3.2.3. Postbaseline Liver-Related Laboratory Abnormalities

Liver-related abnormalities that are post Study Baseline within Part 1 and Whole Study periods, and that are post Part 2 Baseline within Co-administration period will be examined and summarized using the number and percentage of subjects who were reported to have the following laboratory test values:

- Aspartate aminotransferase (AST): (a) > 3 × ULN, (b) > 5 × ULN, (c) > 10 × ULN,
 (d) > 20 × ULN
- ALT: (a) $> 3 \times ULN$, (b) $> 5 \times ULN$, (c) $> 10 \times ULN$, (d) $> 20 \times ULN$
- AST or ALT: (a) $> 3 \times ULN$, (b) $> 5 \times ULN$, (c) $> 10 \times ULN$, (d) $> 20 \times ULN$

- Total bilirubin: (a) $> 1 \times ULN$, (b) $> 2 \times ULN$
- Alkaline phosphatase (ALP) $> 1.5 \times ULN$
- AST or ALT > $3 \times ULN$ and total bilirubin: (a) > $1.5 \times ULN$, (b) > $2 \times ULN$
- AST or ALT $> 3 \times ULN$, total bilirubin $> 2 \times ULN$, and ALP $< 2 \times ULN$

The summary for an administration period will include all postbaseline data up to the safety cutoff date of the period. For individual laboratory test, subjects will be counted once based on the most severe postbaseline value. For both the composite endpoint of AST or ALT and total bilirubin, and the composite endpoint of AST or ALT, total bilirubin, and ALP, subjects will be counted once when the criteria are met at the same postbaseline visit date. The denominator is the number of subjects in the safety analysis set with nonmissing postbaseline value of the tests in evaluation at the same postbaseline visit date.

Subjects with AST or ALT > 3 × ULN, total bilirubin > 1 × ULN, or ALP > 1.5 × ULN will be listed with HCV RNA (log_{10}).

7.3.3. Renal-Related Laboratory Evaluations

All renal safety data will be analyzed using Safety Analysis Sets, unless otherwise specified.

7.3.3.1. Serum Creatinine and eGFR_{CG}

Baseline, postbaseline and change from baseline in serum creatinine and $eGFR_{CG}$ at each visit will be summarized by treatment group and overall using descriptive statistics for safety periods Part 2 and Whole Study periods, respectively. The following formulae will be used to calculate eGFR:

Cockroft-Gault

```
eGFRCG (mL/min) = [(140 - age (years)) \times weight (kg) \times (0.85 \text{ if female})] / (SCr (mg/dL) \times 72),
```

where weight is total body mass in kilograms, and SCr is serum creatinine.

Median (Q1, Q3) of change from baseline in serum creatinine and eGFR_{CG} over time will be plotted by treatment group and overall.

7.3.3.2. Proteinuria by Urinalysis (Dipstick)

The proteinuria by urinalysis (dipstick) toxicity grade (Grade 0 to Grade 3) at each postbaseline visit will be summarized by baseline proteinuria toxicity grade for both treatment groups and overall.

7.3.3.3. Proteinuria by Quantitative Assessment

The baseline, postbaseline, changes from baseline, and percentage change from baseline in urine protein to creatinine ratio (UPCR) and urine albumin to creatinine ration (UACR) will be summarized by visit, treatment group and overall using descriptive statistics.

The number and percentage of subjects with UPCR ≤ 200 mg/g versus > 200 mg/g {KDIGO Guideline Development Staff 2013} will be summarized by baseline category at each visit.

The number and percentage of subjects with UACR < 30 mg/g versus ≥ 30 mg/g {KDIGO Guideline Development Staff 2013} will be summarized by baseline category at each visit.

7.3.3.4. Renal Safety Tests: Urine Retinol Binding Protein (RBP) to Creatinine Ratio and Beta-2-microglobulin to Creatinine Ratio

Baseline, postbaseline, change from baseline and percentage change from baseline in renal safety tests, including urine retinol binding protein (RBP) to creatinine ratio and beta-2-microglobulin to creatinine ratio, will be summarized for both treatment groups and overall, by visit using descriptive statistics.

7.3.3.5. Other Renal Safety Data

Baseline, postbaseline, change from baseline in urine creatinine will be summarized by treatment group and visit using descriptive statistics, for both Whole Study and Part 2 periods.

7.3.4. Bone Laboratory Evaluations

Baseline, postbaseline, and change from baseline in bone biomarkers PTH and serum OH-25 vitamin D will be summarized by treatment group and visit using descriptive statistics, for both Whole Study and Part 2 periods.

7.3.5. Body Weight, Height and Vital Signs

Vital signs (systolic and diastolic blood pressure [mmHg], pulse [beats/min]) at each visit, and change from baseline at each visit will be summarized for both Whole Study and Part 2 periods using descriptive statistics (n, mean, SD, median, Q1, Q3, minimum, and maximum) by treatment group and overall. The baseline value will be defined as the last available value collected on or prior to the date/time of first dose of study drug (HIV drug when summarizing for Whole Study period, LDV/SOF when summarizing for Part 2). Change from baseline to a postbaseline visit will be defined as the postbaseline value minus the baseline value.

In the case of multiple values in an analysis window, data will be selected for analysis as described in Section 3.8.3. No inferential statistics will be generated.

A by-subject listing of vital signs (systolic and diastolic blood pressure [mmHg], pulse [beats/min], respiration [breaths/min], and body temperature [°C]) will be provided by subject ID number and visit in chronological order. In the same manner, a by-subject listing of body weight, height, and BMI will be provided separately.

7.4. Prior and Concomitant Medications

7.4.1. Nonstudy Drug Antiretroviral Medications

Any nonstudy drug ARV medications used prior to, during, or after the study (if collected) will be coded using the GSI-modified World Health Organization (WHO) Drug Dictionary. The WHO preferred name and drug code will be attached to the clinical database. All nonstudy drug ARV medications will be listed. No inferential statistics will be provided.

7.4.2. Concomitant Non-ARV Medications

Concomitant non-ARV medications (ie, medications other than study drug that are taken while receiving either LDV/SOF or HIV study drug) will be coded using the WHO Drug Dictionary. The WHO preferred name and drug code will be attached to the clinical database. Use of concomitant medications from Study Day 1 up to the maximum of HIV study drug last dose dates and LDV/SOF last dose date will be summarized (number and percentage of subjects) by treatment group and overall, WHO drug class and preferred name. Multiple drug use (by preferred name) will be counted only once per subject. The summary will be sorted alphabetically by drug class and then by decreasing total frequency within a class.

If the start or stop date of non-ARV medications is incomplete, the month and year (or year alone, if month is not recorded) of the start or stop date will be used to determine whether the non-ARVs are concomitant or not. The medication is concomitant if the month and year of the start or stop (or year of the start or stop, if month is not recorded) of the medication does not meet either of the following criteria:

- The month and year of start (or year of start if month is not recorded) of the medication is after both LDV/SOF last dose date and HIV study drug last dose date
- The month and year of stop (or year of stop if month is not recorded) of the medication is before both LDV/SOF first dose date and HIV study drug first dose date

If the start and stop date of non-ARV medications are complete, the start date is not after both last dose dates of the study drugs and the stop date is not before both first dose date, or the non-ARV medications are marked as ongoing and start date is on or before both last dose date, the non-ARV medications are concomitant.

Summaries of non-ARV concomitant medications will be provided by treatment group and overall, for Whole Study period only. Subjects with any non-ARV concomitant medications will be listed. No inferential statistics will be provided.

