3.4. Duration of Treatment

The HIV treatment duration is from the Day 1 visit until the last study visit at the Post-HCV Treatment Week 12. The HCV treatment duration is 12 weeks. Screening assessments will be completed within 42 days of the Day 1 visit.

All subjects will complete the following study visits: Screening, Day 1, Weeks 4, 6 (laboratory visit only), 8 (start of HCV treatment), 12, 16, and 20 (end of HCV treatment), and post-HCV treatment visits 4 and 12 weeks after the last LDV/SOF dose.

Subjects who complete the study through the last study visit at the Post-HCV Treatment Week 12 visit will be required to return to the clinic 30 days after the completion of the study treatment for a 30-Day Follow-Up visit.

- a Following the Day 1 visit, subjects will return for study visits at Weeks 4, 6 (laboratory visit only), 8, 12, 16, 20, and Post-HCV Treatment 4 and 12 weeks after the last LDV/SOF dose.
- b Part 1: subjects are randomized to either E/C/F/TAF FDC or F/R/TAF FDC on Day 1 and maintain HIV treatment to the Week 8 visit.
- c Part 2: At Week 8, once HIV-1 RNA suppression (< 50 copies/mL) is confirmed (based on the Week 6 HIV-1 RNA value), subjects will start on LDV/SOF FDC for 12 weeks (until Week 20) while maintaining their HIV treatment. At Week 20, LDV/SOF FDC will be discontinued while continuing HIV treatment. Subjects will continue in the study for another 12 weeks to determine SVR4 (4 weeks post-HCV treatment) and SVR12 (12 weeks post-HCV treatment).

- d Subjects who complete the study through the Post-HCV Treatment Week 12 visit will be required to return to the clinic 30 days after the completion of the study treatment for a 30-Day Follow-Up Visit.
- e At the Day 1 visit, subjects will switch to either E/C/F/TAF FDC or F/R/TAF FDC and continue on HIV treatment until the last study visit at the Post-HCV Treatment Week 12 visit.

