c) The corrected UP results will be used for the following analysis and referred as "UP" in following text. If AVALC of the corrected UP is "< 4.0", the AVAL of the corrected UP will be imputed as 3.9 mg/dL.

Unit conversion for renal safety tests derived from related tests with conventional units

- a) Urine RBP (ug/L) to creatinine (mg/dL) ratio: $1 (ug/L) / (mg/dL) = 100 \times ug/g$
- b) Urine Beta-2-microglobulin (mg/L) to creatinine (mg/dL) ratio: $1 \text{ (mg/L)} / \text{ (mg/dL)} = 10^5 \text{ ug/g}$
- c) Urine Protein (mg/dL) to creatinine (mg/dL) ratio: 1 (mg/dL) / (mg/dL) = 1000 x mg/g
- d) Urine Albumin (mg/dL) to creatinine (mg/dL) ratio: 1 (mg/dL) / (mg/dL) = 1000 x mg/g

Calculation of ratios:

To calculate laboratory ratios (eg, urine RBP to creatinine ratio), the lab value of each test in the ratio needs to be from the same accession number; if any test value used for the ratio calculation from the same accession number is missing, then the ratio is not calculable (ie, missing). For urine creatinine, a value of "< 1" is handled as a missing value in the calculation of related ratios. For urine protein, a value of "< 4.0" is handled as a missing value in the calculation of UPCR.

Combined category of UP and UPCR

- a) First merge UP and UPCR based on the subject identifier and accession number.
- b) At each visit, based on UP to select which pair of records should be used for the analysis. That is, once a UP record is selected for that visit, the UPCR with the same accession number (if calculated) will be selected. Please note, UPCR is missing when UP < 4.0 mg/dL.
- c) Subject will be classified as "UPCR ≤ 200 mg/g" if UP < 4.0 mg/dL or UPCR ≤ 200 mg/g; Subject will be classified as "UPCR > 200 mg/g" if UPCR > 200 mg/g; Otherwise, subject will be classified as "Missing".
- 16) Concomitant nonstudy-drug ARV medications (ie, ARV medications other than study drug that are taken while receiving study drug) will be flagged in "Nonstudy-Drug Antiviral Medication" listing. The logic to define concomitant nonstudy-drug ARV is similar to concomitant non-ARV Medications (see details in Section 7.4.2).
- 17) Age for laboratory test reference range will be based on the age at the sample collection date.

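### SAP 7.4.2: the clause for ongoing medications cuts off at the earlier last dose, so ongoing drugs started between the two last doses drop out of the concomitant medication table

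*SAP*

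**What the plan says.** SAP 7.4.2 makes five statements that bear on which medications are counted.

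- **Definition.** Concomitant non-ARV medications are "medications other than study drug that are taken while receiving either LDV/SOF or HIV study drug".
- **Summary period.** The table covers "Use of concomitant medications from Study Day 1 up to the maximum of HIV study drug last dose dates and LDV/SOF last dose date".
- **Incomplete dates.** A record is dropped for starting too late only when the start "of the medication is after both LDV/SOF last dose date and HIV study drug last dose date".
- **Complete start and stop dates.** A record passes the start test when "the start date is not after both last dose dates of the study drugs".
- **Ongoing.** A record with no stop date passes when "the non-ARV medications are marked as ongoing and start date is on or before both last dose date".

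SAP 7.1.1 assigns this table to the Whole Study period, which Table 7-1 ends at the later of the two last-dose dates.

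On non-study antiretrovirals, SAP 7.4.1 lists all of them. Appendix 4 item 16 adds a flag for those taken while on study drug and says: "The logic to define concomitant nonstudy-drug ARV is similar to concomitant non-ARV Medications".

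The two last-dose dates differ by design. Protocol 3.4 states that "subjects will start on LDV/SOF FDC for 12 weeks (until Week 20) while maintaining their HIV treatment", and that HIV study drug then continues to the Post-HCV Treatment Week 12 visit.

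**The concern.** Four of the five statements point to the later last dose. The ongoing clause alone points to the earlier one. Two subjects who start the same drug on the same day during post-LDV/SOF follow-up would be classified differently because one stopped it and the other did not. Nothing in the SAP gives a reason for that.

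The undercount would have a direction. It falls on drugs begun in the last 12 weeks of HIV treatment and still being taken, which are the records most likely to be marked ongoing. The table would then understate use against its own definition. If item 16 is programmed with the same clause, a non-study antiretroviral begun in that span and continued would appear in its listing without the concomitant flag.

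A related gap concerns subjects who leave in Part 1. They belong to the Safety Analysis Set (SAP 3.1.3.1) but have no LDV/SOF dates. All three date rules refer to both drugs, and none says what to do when one drug was never taken.

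**Working it through.** The plan states no figure here to reproduce. The check compares the date rules and then counts days.

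**Rules as conditions.** Let S be the medication start, L the last LDV/SOF dose and H the last HIV study drug dose.

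- Incomplete dates: drop for lateness if S > L and S > H, so keep if S ≤ max(L, H), to the precision of the month or year recorded.
- Complete dates: start not after both, so keep if S ≤ max(L, H). The English could also be read as after neither, but the incomplete-date rule, written as an exclusion, settles the sense.
- Ongoing: S ≤ L and S ≤ H, so keep if S ≤ min(L, H).

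The rules disagree for S from min(L, H) + 1 to max(L, H), a gap of |H − L| days.

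**Inputs.** Week 20 is nominal Day 140 and Week 32 is nominal Day 224 (SAP Table 3-1). LDV/SOF is assumed to run 84 days from Day 57, with HIV study drug stopping 84 days after the last LDV/SOF dose (Protocol 3.4). Protocol 6.9.1 allows LDV/SOF to start 2 to 4 weeks late when HIV-1 RNA must be repeated after Week 6. The Week 24 snapshot window is Days 155 to 196 (SAP 6.2.2.2), that is 196 − 155 + 1 = 42 days.

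| Case | L | H | Start days lost if ongoing | Share of days on HIV study drug | Snapshot window days in gap |
|---|---|---|---|---|---|
| Nominal | 140 | 224 | 141–224 (84) | 84/224 = 37.5% | 42 of 42 |
| LDV/SOF 2 weeks late | 154 | 238 | 155–238 (84) | 84/238 = 35.3% | 42 of 42 |
| LDV/SOF 4 weeks late | 168 | 252 | 169–252 (84) | 84/252 = 33.3% | 196 − 169 + 1 = 28 of 42 |
| LDV/SOF stopped at Day 84 (illustration) | 84 | 168 | 85–168 (84) | 84/168 = 50% | 168 − 155 + 1 = 14 of 42 |

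The gap also opens the other way. If HIV study drug stopped on, say, Day 100 and LDV/SOF ran to Day 140, as Protocol 6.5.1 permits, ongoing drugs started on Days 101 to 140 (140 − 100 = 40 days) would be lost.

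**After the fix.** With S ≤ max(L, H) for ongoing records, all 224 nominal start days qualify, against 140 under the literal text. The gap is 0 days.

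**The case against.** The strongest reply is that the intended rule is already plain. The definition, the summary period, the other two date rules and Table 7-1 all agree, so the ongoing clause looks like a slip for the complete-date wording, and a careful programmer would probably read it that way. That is fair, and it keeps the point minor. It does not remove it, because the clause is a stated classification rule and following it as written gives a different count.

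Three stronger readings are tempting, and the documents do not support them.

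- *Everything started after LDV/SOF ends is lost.* Only records marked ongoing are affected. Those with complete dates are kept, as are those handled under the incomplete-date rule. Each preferred name counts once per subject, so restarting a drug already counted changes nothing.
- *Added antiretrovirals are hidden during the Week 24 window, so the HIV result is in doubt.* SAP 7.4.1 lists every non-study antiretroviral, so at most a flag is missing. Item 16 calls its logic similar, not identical, so even that is an inference. The snapshot algorithm in SAP 6.2.2.2 uses on-treatment HIV-1 RNA and the reason for discontinuation; it has no term for other antiretrovirals. Protocol 5.4 prohibits other HIV medication, so an antiretroviral added alongside HIV study drug would be a deviation, and the documents give no frequency for it.
- *Over a third of medications are missed.* The 37.5% is a share of calendar days. The documents give no rate at which ongoing medications are newly started.

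The missing LDV/SOF date for Part 1 leavers also cannot be charged to the ongoing clause alone, since all three date rules share it.

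**Conclusion.** The inconsistency is real and minor. As written, the ongoing clause contradicts the definition, the summary period and the two other date rules in its own section. It would leave ongoing non-ARV medications started between the two last doses out of a planned Whole Study safety table: nominally Study Days 141 to 224, or 84 start days. How many medications that means is unknown.

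The same clause could cost an ongoing non-study antiretroviral its flag under Appendix 4 item 16, though not its place in the listing. The consequence stops at one descriptive table without inference and one listing flag. No endpoint, hypothesis test, sample size or power depends on it.

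The conclusion rests on reading the clause literally. The day counts rest on the nominal visit schedule and on HIV study drug ending 12 weeks after the last LDV/SOF dose. A delayed LDV/SOF start moves the gap and reduces its overlap with the snapshot window, but its length stays at 84 days.

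**What to change.** Make three wording changes.

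1. In SAP 7.4.2, replace the ongoing condition with: *marked ongoing, with a start no later than the later of the last HIV study drug dose and the last LDV/SOF dose*.
2. In the same section, state that for subjects never dosed with LDV/SOF all the date rules use the HIV study drug dates only.
3. In Appendix 4 item 16, replace the reference to similar logic with the same later-date rule.

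Item 16 should not be tied to the HIV study drug dates alone. Protocol 6.5.1 and 6.9.1 foresee replacement antiretrovirals taken with continuing LDV/SOF after HIV study drug has stopped. Those are taken while on study drug, and a rule using only HIV study drug dates would leave them unflagged.

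The cost is a phrase or sentence in each place. No new data are needed, and no hypothesis or planned test changes.
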